7.0 Trial Objectives

7.1 Primary Objectives:

7.1.1 Primary Safety Objective

- To evaluate the safety (in all subjects) and reactogenicity (in a subset of subjects) of CVnCoV administered as a 2-dose schedule to adults 18 years of age or older.

7.1.2 Primary Immunogenicity Objective

- To assess antibody responses to the receptor-binding domain (RBD) of S protein of SARS-CoV-2 after 1 and 2 doses of CVnCoV in adults 18 years of age or older included in a subset of subjects.

7.2 Secondary Objectives:

7.2.1 Secondary Efficacy Objectives

- To assess the efficacy of a 2-dose schedule of CVnCoV in the prevention of first episodes of virologically-confirmed symptomatic cases of COVID-19 of any severity in SARS-CoV-2 naïve subjects.
- To describe the severity of first episodes of virologically-confirmed symptomatic cases of COVID-19 in SARS-CoV-2 naïve subjects, receiving a 2-dose schedule of CVnCoV compared to those administered placebo.
- To assess the efficacy of a 2-dose schedule of CVnCoV in reducing the BoD from COVID-19.

7.2.2 Secondary Immunogenicity Objectives

- To assess SARS-CoV-2 virus neutralizing antibody responses after 1 and 2 doses of CVnCoV in adults 18 years of age or older included in a subset of subjects.

8.0 Trial Design

8.1 Overall Design

Trial CV-NCOV-005 is conducted as a randomized, observer-blinded, and placebo-controlled trial. Subjects 18 years of age or older previously enrolled in the non-interventional trial performed at the Mainz University, Germany (COVID19-5-P-002), other health care workers (HCW) and potentially students in clinical training are enrolled. Subjects receive a 2-dose schedule, 28 days apart, of either one of two lots of CVnCoV at a dose level of 12 µg mRNA or placebo (normal saline [0.9% NaCl] for injection) in a 1:1:1 ratio. Approximately 2,520 subjects (840 per randomization group) are enrolled.

The safety, reactogenicity and immunogenicity of a 2-dose schedule of CVnCoV in HCWs is assessed descriptively.

The primary safety objective is to expand the safety database that demonstrates the safety profile of CVnCoV. The safety and reactogenicity of a 2-dose schedule of CVnCoV is assessed in detail by measuring the frequency and severity of solicited local and systemic AEs (on the day of vaccination and for the following 7 days after each vaccination) and unsolicited AEs on the day of vaccination and for the following 28 days after each vaccination, both in a subset of subjects (Immunogenicity/Reactogenicity Subset i.e. the first 1,260 subjects enrolled). Medically-attended AEs through 6 months after the second trial vaccination and AESIs, Serious Adverse Events (SAEs) and AEs leading to vaccine withdrawal or trial discontinuation for 1 year after the second trial vaccination are collected for all subjects.

An independent Data Safety Monitoring Board (DSMB, see Section 8.4) performs a review of the available safety data of both CV-NCOV-004 and CV-NCOV-005 at regular meetings.

The immunogenicity of CVnCoV after 1 and 2 doses is evaluated in a subset of subjects (Immunogenicity/Reactogenicity Subset, the first 1,260 subjects enrolled) by measuring:

- binding antibodies to the SARS-CoV-2 RBD of S protein
- viral neutralizing antibodies directed against SARS-CoV-2

During the trial, subjects undergo active surveillance for COVID-19. Subjects suspected of having COVID-19 undergo testing for SARS-CoV-2 virus.

8.2 Interim Analysis

No formal IA is done. In August 2021 a first immunogenicity delivery is provided. PRA/ICON who is to create that analysis is unblinded on that occasion.

8.3 End of Trial

A subject is considered to have completed the trial when he/she has completed all visits, procedures, and tests applicable for the group to which he/she was randomized to at trial entry. Exception: Placebo subjects discontinue the trial once study protocol version 3.0 and 4.0 are approved. The corresponding wording from the protocol is as follows: *“After trial unblinding, i.e. after approval of study protocol version 3.0 and 4.0, all placebo subjects should be withdrawn at the earliest possible timepoint, if their originally planned End of Trial visit is later than February 2022 and will undergo the same procedures as for the End of Trial visit at their withdrawal visit. If a withdrawal visit cannot be scheduled for placebo subjects due to the pandemic setting, the end of trial assessment, i.e. collection of final safety data, can also be done by phone. In the e-*

CRF, the withdrawal reason for placebo subjects should be documented as “placebo subject withdrawn after trial unblinding”.

End of Trial (EOT) is defined as the point at which the last subject has completed the last visit on Day 393 or (prematurely) discontinued the trial.

8.4 Independent Data Safety Monitoring Board

An independent DSMB is convened to oversee the safety of subjects participating in this trial and trial CV-NCOV-004, to assess the progress and conduct of the trials, to review the cumulative safety data from the trials, and to make recommendations to CureVac whether to continue, modify, or stop the trials.

The DSMB has regularly scheduled meetings to perform these responsibilities. During these meetings, the DSMB is informed of the safety data being generated in other ongoing clinical trials of CVnCoV. In addition to safety data, the DSMB is asked to review efficacy data at the interim analyses and possibly at other time points during the trial for a continued assessment of the risk-benefit of the trial. As part of the risk-benefit analysis, the DSMB periodically monitors COVID-19 cases for signals of Vaccine Dependent Disease Enhancement (VDE).

The DSMB Charter describes in detail the composition and objectives of the DSMB, the responsibilities of the DSMB, CureVac and PRA/ICON, the schedule and conduct of the DSMB meetings, the datasets to be reviewed, and the stopping criteria for the trial. The Charter contains the SAP for the DSMB.

8.5 Sample Size Considerations

8.5.1 Sample Size Considerations for the Primary Safety Objective

While solicited vaccine reactions are expected, AEs that would limit product development may arise. Table 1 below indicates the probability of observing at least 1 AE in the trial when the true incidence of the AE with CVnCoV is 1:1000, 5:1000 or 1:100.

Table 1 Probability of Observing at least one Adverse Event Given a True Incidence Rate

True AE Incidence	All Subjects	Subset for solicited/ unsolicited AE	Subset for solicited/ unsolicited AE
	Pooled Lots (N=1,680)	By Lot (N=420)	Pooled Lots (N=840)
1:1000	81.4%	34.3%	56.8%
5:1000	100.0%	87.8%	98.5%
1:100	100.0%	98.5%	100.0%

N = Number of Subjects receiving CVnCoV

With a total of 1,680 subjects receiving CVnCoV (840 per lot), AEs with a true incidence of 1:1000 are likely observed in this trial, with a 81.4% probability of observing at least one. Additionally, observation of 0 AEs in 1,680 subjects would be associated with a 95% confidence that the true incidence rate of this AE is below 1.8:1000. With a total of 840 subjects included in the Immunogenicity/Reactogenicity subset and receiving CVnCoV (420 per lot), solicited/unsolicited AEs with a true incidence of 5:1000 are likely observed in this trial with a 98.5% probability of observing at least one. Observation of 0 AE in 840 subjects would be associated with a 95% confidence that the true incidence rate of this AE is below 3.6:1000.

8.5.2 Sample for the Primary Immunogenicity Objective

The primary analysis for SARS-CoV-2 RBD of S protein antibody response performed on data collected on Days 1, 29 and 43 is done on 250 subjects (200 on verum, i.e. 100 per lot and 50 on placebo) from the Per Protocol Immunogenicity (PPI) analysis set.

8.6 Randomization and Blinding

The trial is randomized, observer-blinded, and placebo-controlled. The difference in appearance of the investigational CVnCoV vaccine and placebo requires the trial to be conducted in an observer-blinded manner.

The pharmacist/personnel preparing the trial vaccine at the site is not blinded to the identity of the trial vaccine being administered to the subject. However, the vaccinator, investigator and all site personnel involved in the conduct of the trial are blinded to trial vaccine and subject treatment assignments. To maintain the blinding of the vaccinator, the unblinded pharmacist/site personnel provide the dose of trial vaccine to the vaccinator pre-filled in a syringe with a label covering the liquid contents so that it is not visible. All personnel at PRA/ICON and Sponsor directly involved in the conduct of the trial is also blinded. There are certain individuals at PRA/ICON and Sponsor whose function requires them to be unblinded during the trial (e.g., unblinded monitoring for trial vaccine accountability in the pharmacy; unblinded independent statistician assisting the DSMB; review of immunogenicity data). These unblinded individuals are identified and their responsibilities documented.

As the immunogenicity results would unblind the subject's treatment assignment, an independent laboratory performing the assays keep the results in strict confidence. An unblinded person, named at the start of the trial and independent of the conduct of the trial, has the responsibility of reviewing the quality of the immunogenicity data as it is being generated. This person maintains the results in strict confidence. To maintain the blind, the immunogenicity data is only merged with the clinical database at CDISC level following unblinding of the trial.

The first immunogenicity analysis is scheduled for August 2021. PRA/ICON who is to perform this analysis is unblinded on that occasion.

Approximately 2,520 subjects 18 years of age or older are enrolled at the site at Mainz University, Germany and are randomized in a 1:1:1 ratio (840 per randomization group) to receive either one of two different lots of a 2-dose schedule of CVnCoV or placebo. The randomization is performed centrally and stratified by age group (18 to 60 and ≥ 61 years of age).

The randomization scheme is generated and maintained by an independent statistical group at PRA/ICON. Subjects are enrolled into the trial online and randomized using an Interactive Web Response System (IWRS). The first 1,260 subjects enrolled are planned to be included in the Immunogenicity/Reactogenicity Subset.

See Section 10.10 for handling of cases where a subject becomes eligible to receive an AV during the course of the trial.

In Study Protocol 3.0 the following decision regarding unblinding was added: "*Since the efficacy results from the HERALD study for CVnCoV are available and all subjects in the CV-NCOV-005 study are currently eligible to receive an authorized vaccine, all subjects in this CV-NCOV-005 study will be unblinded.*" This unblinding is performed on a by-subject level via IWRS and therefore does not require any additional programmatic or planning attention.

In July 2021, on the occasion of Herald CV-NCOV-004 study primary efficacy analysis delivery, selected members from the Sponsor and PRA/ICON study teams (i.e. both Biostatistics teams) were unblinded for CV-NCOV-005. In December 2021 the full Sponsor and PRA/ICON study teams were unblinded.

9.0 Trial Endpoints

9.1 Primary Endpoints

9.1.1 Primary Safety Endpoints

- Occurrence, intensity and relationship of medically-attended AEs collected through 6 months after the second trial vaccination in all subjects.

-
- Occurrence, intensity and relationship of SAEs and AESIs collected through EOT Visit in all subjects.
 - Occurrence of fatal SAEs through EOT Visit in all subjects.
 - Occurrence of AEs leading to vaccine withdrawal or trial discontinuation through EOT Visit in all subjects.
 - Occurrence, intensity and duration of each solicited local AE within 7 days after each trial vaccination in a subset of subjects.
 - Occurrence, intensity, duration of each solicited systemic AE within 7 days after each trial vaccination in a subset of subjects.
 - Occurrence, intensity and relationship of unsolicited AEs occurring within 28 days after each trial vaccination in a subset of subjects.

9.1.2 Primary Immunogenicity Endpoints

SARS-CoV-2 RBD of the S protein antibody responses on Days 1, 29 and 43 in a subset of 250 subjects (Per Protocol Immunogenicity Set (PPI)) :

- Serum antibodies to SARS-CoV-2 RBD of the S protein
- Occurrence of seroconversion to SARS-CoV-2 RBD of S protein.

Thereby, seroconversion is defined as detectable SARS-CoV-2 RBD of S protein antibodies in the serum of subjects who tested seronegative at Day 1 (Baseline), see Section 10.6.2.1 and Section 10.6.1 for details.

9.2 Secondary Endpoints

9.2.1 Secondary Efficacy Endpoints

- Occurrence of first episodes of virologically-confirmed (RT-PCR positive) symptomatic cases of COVID-19 of any severity meeting the case definition for the efficacy analysis.
- Occurrence of first episodes of virologically-confirmed (RT-PCR positive) symptomatic mild cases of COVID-19 meeting the case definition for the efficacy analysis as defined in Section 10.7.3.
- BoD scores calculated based on first episodes of virologically-confirmed (RT-PCR positive) cases of COVID-19 of any severity meeting the case definition for the efficacy analysis.
 - BoD #1 – no disease (not infected or asymptomatic infection) = 0; mild or moderate disease = 1; severe disease = 2.
 - BoD #2 – no disease (not infected or asymptomatic infection) = 0; disease without hospitalization = 1; disease with hospitalization = 2; death = 3.

9.2.2 Secondary Immunogenicity Endpoints

- SARS-CoV-2 viral neutralizing antibody responses on Days 1, 29 and 43 in the PPI subset of 250 subjects:
 - Serum viral neutralizing antibodies to SARS-CoV-2 virus, as measured by a virus neutralizing assay.

- o Occurrence of seroconversion to SARS-CoV-2 virus as measured by a virus neutralizing assay.

Thereby, seroconversion is defined as detectable SARS-CoV-2 viral neutralizing antibodies in the serum of subjects who tested seronegative at Baseline, see Section 10.6.2.2 and Section 10.6.1 for details.

9.3 Exploratory Endpoints

9.3.1 Exploratory Efficacy Endpoint

In agreement with the sponsor it was decided not to analyze the exploratory efficacy endpoint in this study.

9.3.2 Exploratory Immunogenicity Endpoints

Exploratory Immunogenicity Endpoints are voided since protocol version 5.0. They have never been analyzed in this study.

9.3.3 Exploratory Efficacy Endpoints (pooled analysis of trial COVID19-5-P-002 and trial CV-NCOV-005)

The exploratory efficacy endpoints related to the pooled analysis of COVID19-5-P-002 and CV-NCOV-005 are voided since protocol version 5.0. They have never been analyzed in this study.

9.4 Estimands

Table 2 **Error! Reference source not found.** presents the study endpoints and corresponding Estimands based on the study protocol, Section 4.3.

Table 2: Study Endpoints and Estimands

ENDPOINTS (subject level)	ESTIMANDS (population level)
Primary Safety	

 • Occurrence, intensity and relationship of medically-attended AEs collected through 6 months after the second trial vaccination in all subjects. • Occurrence, intensity and relationship of SAEs and AESIs collected through EOT Visit in all subjects. • Occurrence of fatal SAEs through EOT Visit in all subjects. • Occurrence of AEs leading to vaccine withdrawal or trial discontinuation through EOT Visit in all subjects. • Occurrence, intensity and duration of each solicited local AE within 7 days after each trial vaccination in a subset of subjects. • Occurrence, intensity, duration and relationship of each solicited systemic AE within 7 days after each trial vaccination in a subset of subjects. 	
In subjects who received at least 1 dose of CVnCoV or placebo vaccine, the number and percentage of subjects by group reporting at least 1 and of each type {by System Organ Class (SOC)/ Preferred Term (PT)} of:
 
 • Medically-attended AE collected through 6 months after the second trial vaccination overall, by intensity and by causal relationship to trial vaccine. • SAE collected through EOT Visit overall and by causal relationship to trial vaccine. • AESI collected through EOT Visit overall, by intensity and by causal relationship to trial vaccine. • Fatal SAE collected through EOT Visit. • At least 1 AE leading to vaccine withdrawal or trial discontinuation through EOT Visit. 
In subjects who received at least 1 dose of CVnCoV or placebo vaccine, and belong to the Immunogenicity/Reactogenicity subset, the number and percentage of subjects by group reporting:
 
 • Each solicited local AE within 7 days after each trial vaccination by intensity and overall.

ENDPOINTS (subject level)	ESTIMANDS (population level)

 Occurrence, intensity and relationship of unsolicited AEs occurring within 28 days after each trial vaccination in a subset of subjects. 	
 Each solicited systemic AE within 7 days after each trial vaccination by intensity, by relationship to trial vaccine and overall. At least 1 unsolicited AE, at least 1 grade 3 unsolicited AE and each unsolicited AE by SOC/PT occurring within 28 days after each trial vaccination and overall by causal relationship to trial vaccine and overall. 
The mean duration in days by group with standard deviation (SD) of solicited AEs is described.

Primary Immunogenicity	

SARS-CoV-2 RBD of S protein antibody responses
 
On Days 1, 29 and 43:
 
 Serum antibodies to SARS-CoV-2 RBD of S protein. Occurrence of seroconversion to SARS-CoV-2 RBD of S protein 
 Seroconversion is defined as detectable SARS-CoV-2 RBD of S protein antibodies in the serum of subjects who tested seronegative at baseline. 	
In subjects belonging to the Immunogenicity/Reactogenicity subset and evaluable {complying with the definition of PPI Subset}:
 
On Days 1, 29 and 43:
 
 Geometric Mean of Titers (GMTs) with 95% Confidence Interval (CI) of SARS-CoV-2 RBD of S protein antibody responses by group and by baseline serostatus. 
On Days 29 and 43 for subjects seronegative at baseline:
 
 Number and percentage with exact 95%CI of subjects by group for whom a seroconversion is observed (detectable SARS-CoV-2 RBD of S protein antibodies in the serum).
Secondary Efficacy	

 Occurrence of first episodes of virologically-confirmed (RT-PCR positive) symptomatic cases of COVID-19 of any severity meeting the case definition for the efficacy analysis. Occurrence of first episodes of virologically-confirmed (RT-PCR positive) symptomatic cases of COVID-19 meeting the case definition for the efficacy analysis by severity (mild, moderate, severe and moderate to severe COVID-19) as defined in the protocol. BoD scores calculated based on first episodes of virologically-confirmed (RT-PCR positive) cases of COVID-19 of any 	
In naïve evaluable subjects {complying with the definition of EAS} at least 15 days following second vaccination:
 
 $VE = 1 - RR$ with exact 95% CI 
Where Relative Risk (RR) is the ratio of attack rates of COVID-19 cases per 100 person-month in the CVnCoV vaccine groups (pooled lots) over the placebo group.
 
In naïve evaluable subjects (complying with the definition of EAS) at least 15 days following second vaccination:
 
 The number and percentage of subjects who developed a first episode of virologically-confirmed (RT-PCR positive) cases of COVID-19 meeting the case definition for the efficacy analysis, by severity (mild, moderate, severe and moderate to severe, as defined in Section 10.7.3.) 
 Descriptive summaries in naïve evaluable subjects (complying with the definition of EAS) at least 15 days following second trial vaccination:

ENDPOINTS (subject level)	ESTIMANDS (population level)
severity meeting the case definition for the efficacy analysis. 
 - BoD #1 – no disease (not infected or asymptomatic infection) = 0; mild or moderate disease = 1; severe disease = 2. - BoD #2 – no disease (not infected or asymptomatic infection) = 0; disease without hospitalization = 1; disease with hospitalization = 2; death = 3. 	
Secondary Immunogenicity	
SARS-CoV-2 virus neutralizing antibody responses in a subset of subjects On Days 1, 29 and 43: 
 • Serum neutralizing antibodies to SARS-CoV-2 virus, as measured by a virus neutralizing assay. • Occurrence of seroconversion to SARS-CoV-2 virus, as measured by a virus neutralizing assay. 
 - Seroconversion is defined as detectable SARS-CoV-2 virus neutralizing antibodies in the serum of subjects who tested seronegative at baseline. 	In subjects belonging to the Immunogenicity/Reactogenicity subset and evaluable (complying with the definition of the PPI): On Days 1, 29 and 43: 
 • GMT with 95% CI of neutralizing antibodies to SARS-CoV-2 virus by group and by baseline sero-status On Days 29 and 43 for subjects seronegative at baseline: 
 • Number and percentage with exact 95%CI of subjects by group for whom a seroconversion is observed (detectable neutralizing antibodies to SARS-CoV-2 virus in the serum).

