12.6.1.3 Analysis of AEs (Combined Unsolicited and Solicited)

An overall summary of unsolicited AEs, SAEs, intercurrent medical conditions affecting immune response, AESIs, medically attended AEs, AEs leading to vaccine withdrawal, AEs leading to withdrawal from trial and AEs with fatal outcome is prepared for AEs occurring within 28 days after each vaccination, within 28 days after any vaccination, and all reported AEs (including those reported at more than 28 days after any vaccination), presenting the number and percentage of subjects with

- any unsolicited AEs ,
- related unsolicited AEs,
- grade 3 (severe) unsolicited AEs
- grade 3 (severe) related unsolicited AEs
- SAEs (includes solicited AEs),
- related SAEs (includes solicited AEs),
- intercurrent medical conditions affecting immune response (includes solicited AEs),
- AESIs (includes solicited AEs),
- related AESIs (includes solicited AEs),
- medically attended AEs (includes solicited AEs),
- related medically attended AEs (includes solicited AEs),

-
- AEs leading to vaccine withdrawal (includes solicited AEs),
 - AEs leading to withdrawal from trial (includes solicited AEs),
 - AEs with fatal outcome (includes solicited AEs),
 - related AEs with fatal outcome (includes solicited AEs).

The overall summary is also provided by gender (male/female) for any vaccination, vaccination 1 and vaccination 2.

The following summaries of AEs by SOC and PT are further provided, separately for AEs occurring within the first 28 days after each vaccination, within the 28 days after any vaccination, and all reported AEs (including those reported at more than 28 days after any vaccination):

- Occurrence of SAEs,
- Occurrence of related SAEs,
- Occurrence of SAEs by maximum severity (mild / moderate / severe),
- Occurrence of related SAEs by maximum severity (mild / moderate / severe),
- Occurrence of intercurrent medical conditions affecting immune response,
- Occurrence of AESIs,
- Occurrence of related AESIs,
- Occurrence of medically attended AEs,
- Occurrence of related medically attended AEs,
- Occurrence of AEs leading to vaccine withdrawal,
- Occurrence of AEs leading to withdrawal from trial,
- Occurrence of AEs with fatal outcome,
- Occurrence of related AEs with fatal outcome,
- Occurrence of SMQs and CMQs (as specified in Section 10.5.7). (The SMQ/CMQ tables are only provided for all reported AEs, not by vaccination 1 and vaccination 2 separately and only by PT, not by SOC.)

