12.6.7 Adapting the Safety Analyses to the Requirements of Extensive Unblinding

If not explicitly exempted, all safety analyses described in Sections 12.6.1 – 12.6.6 are performed under the conditions of data censoring (described in Section 10.10).

In order to maximally maintain the previous analysis setup while nevertheless aiming at optimally evaluating the collected data the following approach is introduced regarding safety analyses.

1. The above-mentioned analyses (Sections 12.6.1 – 12.6.6) remain unchanged, regardless of extensive unblinding. All definitions still correctly apply and analyses are conducted as originally planned and described above.
2. Additional outputs are planned to account for the massive loss of data due to censoring. The concerned analyses are explicitly listed at the end of this Section 12.6.7.
 - a. These additional outputs are closely following the above mentioned safety analyses.
 - b. As far as possible, endpoint definitions and analysis sets are maintained as described in Sections 12.6.1 – 12.6.6.
 - c. No censoring due to unblinding and/or AV receipt is performed.
 - d. AEs/vital sign values are divided into 4 groups: Placebo-only, CVnCoV-only, CVnCoV-AV, AV-only.

AEs/vital sign values are allocated to treatment groups as follows:

- Placebo-only: Only placebo has been administered before AE start date / vital signs date. No CVnCoV and no AV must have been administered until then.

- CVnCoV-only: At least one dose of CVnCoV and no AV has been administered before AE start date / vital signs date. Placebo might have been administered as well.
- CVnCoV-AV: At least one dose of CVnCoV and at least one dose of AV has been administered before AE start date / vital signs date. Placebo might have been administered as well.
- AV-only: At least one dose of AV and no CVnCoV has been administered before AE start date / vital signs date. Placebo might have been administered as well.

Treatments are considered “as received”, not “as randomized”.

The following analyses are repeated as described above. All repeat analyses are based on the SAS.

- Overall summary of unsolicited AEs occurring through EOT Visit
- Unsolicited AEs, SAEs, unsolicited AESIs and AEs with fatal outcome, by SOC and PT occurring through EOT Visit

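### The primary estimands ask for intensity of medically-attended AEs and AESIs, but the SAP specifies no intensity table for either, nor a separate uncensored end-of-trial SOC/PT table for medically-attended AEs

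*SAP*

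**What the plan says.** SAP 9.1.1 defines two of the primary safety endpoints as "Occurrence, intensity and relationship of medically-attended AEs collected through 6 months after the second trial vaccination in all subjects" and "Occurrence, intensity and relationship of SAEs and AESIs collected through EOT Visit in all subjects". Protocol 4.2.1 names the same components.

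SAP 9.4 turns these into numbers and percentages of subjects by group, by SOC and PT. For medically-attended AEs it asks for "Medically-attended AE collected through 6 months after the second trial vaccination overall, by intensity and by causal relationship to trial vaccine". For AESIs it asks for "AESI collected through EOT Visit overall, by intensity and by causal relationship to trial vaccine". For SAEs it asks only for "SAE collected through EOT Visit overall and by causal relationship to trial vaccine". Protocol 4.3 makes the same distinction.

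The outputs are in SAP 12.6.1.3. For the two classes at issue, its SOC/PT tables are all events and related events, the latter listed as "Occurrence of related medically attended AEs" and "Occurrence of related AESIs". SAEs also get all-event and related-event tables by maximum severity.

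SAP 10.10 censors safety data from the first day after unblinding or receipt of an authorized vaccine (AV). SAP 12.6.7 acknowledges that this costs a large amount of data and adds uncensored outputs. Its SOC/PT list reads "Unsolicited AEs, SAEs, unsolicited AESIs and AEs with fatal outcome, by SOC and PT occurring through EOT Visit", and 12.6.1.4 carries the same list.

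**The concern.** When an estimand is stated as overall, by intensity and by relationship, the analysis section should contain a table for each part. Here the intensity part has none for medically-attended AEs or AESIs. The class that does get severity tables is the one whose estimand does not request them, although the SAE endpoint wording in 9.1.1 does mention intensity. That pattern looks like an oversight.

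The second gap concerns the time window. Medically-attended AEs are a six-month endpoint, yet their dedicated tables are censored. CVnCoV recipients who take an AV are asked to stay in safety follow-up, and protocol Table 2 keeps collecting medically-attended AEs through Day 211. So data are gathered after censoring for an endpoint that has no separate uncensored SOC/PT table.

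At stake is whether the final report, produced exactly as the SAP text reads, would present these parts of the primary safety estimand at all.

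**Working it through.** The point rests on matching estimands to specified tables, not on a calculation.

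**Step 1: intensity.**

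| Class | Intensity in endpoint (9.1.1) | Intensity in estimand (9.4) | Dedicated severity table (12.6.1.3) |
|---|---|---|---|
| Medically-attended AEs | yes | yes | none |
| AESIs | yes | yes | none |
| SAEs | yes | no | yes, all and related |

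The overall summary in 12.6.1.3 does not fill the gap. Its grade 3 rows are for unsolicited AEs as a whole; medically-attended AEs and AESIs appear only as any and related.

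**Step 2: nearest substitute.** SAP 12.6.1.1 tabulates all unsolicited AEs by SOC/PT and maximum severity; the version covering all reported events is on the full Safety Analysis Set. Medically-attended AEs and AESIs that are unsolicited fall inside it but are not marked as such. The match is also inexact, because the medically-attended and AESI rows of the overall summary include solicited events and the pooled tables do not.

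**Step 3: uncensored end-of-trial outputs.**

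| Section | Overall summary | SOC/PT tables | Separate medically-attended AE table |
|---|---|---|---|
| 12.6.1.4 | through 28 days after any dose | unsolicited AEs, SAEs, unsolicited AESIs, fatal AEs | no |
| 12.6.7 (four exposure groups) | through the EOT Visit | same list | no |

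If the overall-summary layout of 12.6.1.3 is reused, medically-attended AEs appear as two count rows, any and related. The summary in 12.6.1.4 stops at 28 days. The one running to end of trial is by exposure group. So no uncensored six-month total by randomized vaccine group is specified. SAP 12.6.6 repeats all safety outputs uncensored, but only for the early delivery at 6 weeks after dose 2, which cannot cover six months.

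**Step 4: declaration.** SAP 6.1 lists 17 changes from protocol. Neither omission is among them.

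**Step 5: what censoring could cost.** The plan's safety figure is a chance of seeing at least one event of true incidence 1:1000 among 1,680 CVnCoV recipients: 1 − (1 − 0.001)^1680 = 81.4%, as stated in SAP 8.5.1. The documents do not say how many subjects are censored. As an assumption only, counting just subjects uncensored for the whole window:

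- 50% remaining (840): 1 − 0.999^840 = 56.8%
- 25% remaining (420): 1 − 0.999^420 = 34.3%
- 10% remaining (168): 1 − 0.999^168 = 15.5%

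This overstates the loss, since subjects censored part-way still contribute time, and the point does not depend on it.

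**The case against.** The strongest reply is that little is missing.

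- **Event types are in the uncensored tables.** The unsolicited-AE SOC/PT tables cover the full safety set through end of trial. Read by its evident intent, SAP 10.5.8 drops medically-attended events from tables only when they start later than 6 months after dose 2.
- **Pooling is partial.** Outside the Immunogenicity/Reactogenicity Subset, and beyond 28 days after a dose, only a few event classes are collected or tabulated, so the pooled tables there are not dominated by ordinary unsolicited AEs.
- **Severity is recorded and listed.** The investigator grades every AE (protocol Appendix 10), and SAP 12.0 and 12.6.1 put all AEs in listings.
- **The mismatch starts in the protocol.** Protocol 10.3.5 lists medically-attended AE and AESI tables with no severity version, against protocol 4.3. SAP 12.6.1.3 follows that layout.
- **The complete output list is elsewhere.** Appendix 4 is maintained outside the SAP and may contain these tables.

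All of this stands, and it rules out a reading a reader might reach: that event types or intensity could not be recovered at all. It does not close the gap. The estimand is a number and percentage for a named class. A pooled table cannot be read out for that class, and a listing is not a summary. An internal inconsistency in the protocol does not remove intensity from the estimand. If Appendix 4 has the tables, the SAP text should say so; if they were dropped on purpose, 6.1 should.

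**Conclusion.** The point holds as a gap between the estimands and the specified outputs. In the SAP text, intensity has no dedicated table for either medically-attended AEs or AESIs, and neither uncensored end-of-trial SOC/PT list gives medically-attended AEs a separate table. Uncensored, that six-month endpoint appears only unlabelled among unsolicited AEs and, at most, as count rows in an overall summary. Protocol 10.3.5 shares the intensity gap. The conclusion assumes the SAP text is followed as written and is silent on Appendix 4.

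Two stronger inferences are not supported.

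- **Medically-attended AEs as the only non-serious events collected in everyone.** SAP 10.5 and protocol 9.3.2 also collect AESIs, AEs leading to vaccine withdrawal or trial discontinuation, and non-serious intercurrent conditions in all subjects.
- **Most subjects censored before six months.** Counting back 180 days from protocol version 3.0 (23 July 2021) gives 24 January 2021. But 23 July is a document date, unblinding was done subject by subject through the IWRS, and dose dates are not given. The share affected is unknown; only the SAP's own acknowledgement of heavy loss can be relied on.

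No formal safety test is planned, so no test result is at risk. The consequence is incomplete reporting of primary safety components.

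**What to change.** - **SAP 12.6.1.3:** add medically-attended AEs and AESIs by SOC/PT and maximum severity, for all and for related events.
- **SAP 12.6.1.4 and 12.6.7:** add medically-attended AEs through 6 months after dose 2 by SOC/PT, without censoring. Attach the same caution about follow-up length as for the existing uncensored tables; placebo recipients leave after unblinding while CVnCoV recipients continue, so exposure time differs between groups.
- **SAP 6.1:** if any of these tables is deliberately not produced, list the omission and the reason. Align Appendix 4 with the SAP text either way, and resolve protocol 10.3.5 against 4.3.

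The cost is a few tables built on the planned SAE severity layouts and severity data already in the eCRF. No new data are needed. SAP version 4.0 was written by an unblinded team, so the additions should be recorded in the change history; they implement estimands already stated and introduce no new analysis question.
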